### **For Part 2 only: Chronic Hepatitis B Patients**

In case of virological breakthrough, an unscheduled visit should be performed within one week of receiving HBV DNA results showing an increase in viral load of greater than one log10 above nadir. At the unscheduled visit, a confirmatory HBV DNA sample and a sample for viral resistance monitoring will be taken (see [Appendix 1](#) and Section [4.6.1.8](#)) and sent to one or several central laboratories or to the Sponsor for analysis. Additional unscheduled visits and assessments will be carried out as determined necessary by the treating physician. The Medical Monitor for the study should be informed as needed.

## **4.7 SUBJECT, STUDY, AND SITE DISCONTINUATION**

### **4.7.1 Subject Discontinuation**

The Investigator has the right to discontinue a HV/patient from RO7020531 or withdraw a HV/patient from the study at any time. In addition, HVs/patients have the right to voluntarily discontinue study drug or withdraw from the study at any time for any reason. Reasons for discontinuation of study drug or withdrawal from the study may include, but are not limited to, the following:

- HV/patient withdrawal of consent at any time.
- Any medical condition that the Investigator or Sponsor determines may jeopardize the HV's/patient's safety if he or she continues in the study.
- Investigator or Sponsor determines it is in the best interest of the HV/patient.
- HV/patient non-compliance.

HVs/patients who discontinue study treatment due to poor tolerability to study drug, or other safety related reasons, will not be replaced. HVs/patients who discontinue study treatment early for non-safety reasons may be replaced to ensure sufficient data to make dose-escalation and drug development decisions.

For Part 1, the decision to replace a subject will be made by a mutual agreement between the Sponsor and Investigator. Further information regarding the replacement policy is provided in Section 6.2.

For Part 2, the decision to replace a patient will be taken by the Sponsor.

#### **4.7.1.1 Discontinuation from RO7020531**

HVs/patients have the right to withdraw from the study at any time for any reason.

The Investigators have the right to withdraw HVs/patients from the study in the event of intercurrent illness, AE, pregnancy in female HVs/patients, for administrative or other reasons. The Sponsor should be informed of HVs'/patients' discontinuations from the study or from the study drug.

#### **Part 1: MAD in Healthy Volunteers**

For an individual subject in the MAD cohorts, dose continuation will not occur if the subject experiences any of the following:

- Clinically significant RO7020531-related changes in safety parameters that are considered not acceptable by the Investigator and/or the Sponsor; or
- Poor tolerability, which is considered to affect the HV's well-being and/or the PK evaluation.

Subjects who discontinue the MAD study prematurely will be asked to return to the clinic for a follow-up visit within 7 days after the last dose of study drug. The primary reason for premature study drug discontinuation should be documented on the appropriate eCRF. HVs who discontinue study drug prematurely for safety reasons will not be replaced.

For dose escalation criteria and stopping rules in SAD/MAD cohorts in Part 1 see Section 3.1.2.1.

## **Part 2: Chronic Hepatitis B Patients**

Individual patients must discontinue RO7020531/placebo if they experience any of the following:

- Safety and tolerability issues, e.g., flu-like symptoms not tolerable and not manageable with symptomatic/*prophylactic* treatment with acetaminophen (*paracetamol*) and/or dose reduction of RO7020531 (*Cohort 4 only*).
- Grade 4 ALT (i.e.,  $\geq 10 \times \text{ULN}$ ) as defined by the Division of Acquired Immunodeficiency Syndrome (AIDS) Table for Grading the Severity of Adult and Pediatric Adverse Events (“DAIDS AE grading table”) ([Appendix 6](#)), confirmed within 48-72 hours.
- Grade 3 ALT (i.e.,  $> 5 \times \text{ULN}$ ) combined with total bilirubin  $> 2 \times \text{ULN}$  (of which  $> 35\%$  is direct bilirubin), or Grade 3 ALT and  $\text{INR} > 1.5$ .
- Grade 4 hematology ( $\text{Hb} < 7.0 \text{ g/dL}$ , absolute neutrophil count  $< 400 /\text{mm}^3$ , absolute lymphocyte count  $< 350/\text{mm}^3$ , or platelets  $< 25,000/\text{mm}^3$ ).
- Any other confirmed (within 48-72h) Grade 3/4 laboratory abnormality deemed clinically significant (based on Investigator’s assessment).
- Development of liver decompensation (ascites, varices, Child-Pugh Class B or C clinical classification).
- Confirmed virological breakthrough after ascertaining that patients are compliant with treatment administration.
- For Cohorts 1, 2 and 3: NUC analogue discontinuation due to safety issues or resistance development.

If 4 or more out of 15 patients (12 receiving RO7020531 and 3 receiving placebo) are discontinued for drug-related safety reasons, enrollment will be halted and safety analysis will be performed. The results of the safety analysis will be provided to IEC/IRB and/or Health Authority, if applicable, before resuming enrollment.

Patients who discontinue study drug before the end of 6-week treatment period:

- Will not resume dosing with RO7020531/placebo. Dosing with NUC analogue in Cohorts 1, 2 and 3 will continue per each patient’s physician discretion and local label.

All prematurely discontinued patients will be asked to come back for an unscheduled visit (see Section 4.6.2.4) to have assessments performed as listed in the SoA (Appendix 1) under “Study Drug Discontinuation / Early Termination”.

All patients who discontinue the study treatment prematurely should complete the 6-week follow-up period (starting from the date of the last dose taken) as per SoA (Appendix 1). The primary reason for premature study drug discontinuation should be documented on the appropriate eCRF.

#### **4.7.1.2 Discontinuation from Nucleos(t)ide Analogue (only for Part 2 Cohorts 1, 2 and 3)**

In case of the development of NUC-resistance and/or NUC-related safety issues, discontinuation of NUC should be performed by each patient’s physician in consultation with Investigator and per NUC local label.

Severe acute exacerbations of hepatitis B have been reported in patients who have discontinued anti-HBV therapy. Patients who discontinue NUC treatment should switch to another anti-HBV treatment at the discretion of each patient’s physician.

If a patient discontinues NUC(s), the study drug (RO7020531/placebo) will also be withdrawn. Follow-up visits and assessments should be performed as listed in the SoA (Appendix 1).

If a patient does not switch to another anti-HBV treatment after a NUC discontinuation, hepatic function should be monitored closely with both clinical and laboratory follow-up for at least several months.

#### **4.7.1.3 Withdrawal from Study**

For withdrawal from the treatment phase in Part 2 see Section 4.7.1.1.

Every effort should be made to obtain information on HVs/patients who withdraw from the study, including withdrawal from the follow-up phase. The primary reason for withdrawal from the study treatment and/or full study (including follow up) should be documented on the appropriate eCRF.

HVs/patients will not be followed for any reason if consent has been withdrawn.

When a HV/patient voluntarily withdraws from the study, or is withdrawn by the Investigator, samples collected until the date of withdrawal will be analyzed, unless HV/patient specifically requests for these to be discarded or local laws require their immediate destruction. A HV’s/patient’s withdrawal from the study does not, by itself, constitute withdrawal of specimens donated to the Research Biosample Repository.

#### **4.7.2 Study and Site Discontinuation**

The Sponsor has the right to terminate this study at any time. Reasons for terminating the study may include, but are not limited to, the following:

- The incidence or severity of AEs in this or other studies indicates a potential health hazard to HVs/patients.
- HV/patient enrollment is unsatisfactory.
- Previously unknown data become available which raise significant concerns about the potential risk to participants from continuation of the study.

The Sponsor will notify the Investigator and Health Authorities if the study is placed on hold, or if the Sponsor decides to discontinue the study or development program.

The Sponsor has the right to replace a site at any time. Reasons for replacing a site may include, but are not limited to, the following:

- Excessively slow recruitment
- Poor protocol adherence
- Inaccurate or incomplete data recording
- Non-compliance with the ICH guideline for Good Clinical Practice

### **5. ASSESSMENT OF SAFETY**

#### **5.1 SAFETY PARAMETERS AND DEFINITIONS**

Safety assessments will consist of monitoring and recording AE, including SAEs and non-serious AEs of special interest; measurement of protocol-specified safety laboratory assessments; measurement of protocol-specified vital signs, ECGs; and other protocol-specified tests that are deemed critical to the safety evaluation of the study.

Certain types of events require immediate reporting to the Sponsor, as outlined in Section 5.1.2 and 5.1.3.

##### **5.1.1 Adverse Events**

According to the ICH guideline for Good Clinical Practice, an AE is any untoward medical occurrence in a clinical investigation HV/patient administered a pharmaceutical product, regardless of causal attribution. An AE can therefore be any of the following:

- Any unfavorable and unintended sign (including an abnormal laboratory finding), symptom, or disease temporally associated with the use of a medicinal product, whether or not considered related to the medicinal product.
- Any new disease or exacerbation of an existing disease (a worsening in the character, frequency, or severity of a known condition), except as described in Section 5.3.5.9.
- Recurrence of an intermittent medical condition (e.g., headache) not present at baseline.

- Any deterioration in a laboratory value or other clinical test (e.g., ECG, X-ray) that is associated with symptoms or leads to a change in study treatment or concomitant treatment or discontinuation from study drug.
- AEs that are related to a protocol-mandated intervention, including those that occur prior to assignment of study treatment (e.g., screening invasive procedures such as biopsies).

### **5.1.2 Serious Adverse Events (Immediately Reportable to the Sponsor)**

A SAE is any AE that meets any of the following criteria:

- Fatal (i.e., the AE actually causes or leads to death).
- Life-threatening (i.e., the AE, in the view of the Investigator, places the HV/patient at immediate risk of death).

This does not include any AE that had it occurred in a more severe form or was allowed to continue might have caused death.

- Requires or prolongs inpatient hospitalization (see Section 5.3.5.10).
- Results in persistent or significant disability/incapacity (i.e., the AE results in substantial disruption of the HV's/patient's ability to conduct normal life functions).
- Congenital anomaly/birth defect in a neonate/infant born to a mother exposed to study drug.
- Significant medical event in the Investigator's judgment (e.g., may jeopardize the HV/patient or may require medical/surgical intervention to prevent one of the outcomes listed above).

The terms "severe" and "serious" are not synonymous. Severity refers to the intensity of an AE (rated as mild, moderate, or severe, or according to a pre-defined grading criteria (see Section 5.3.3); the event itself may be of relatively minor medical significance (such as severe headache without any further findings).

Severity and seriousness need to be independently assessed for each AE recorded on the eCRF.

SAEs are required to be reported by the Investigator to the Sponsor immediately (i.e., no more than 24 hours after learning of the event; see Section 5.3.8 for reporting instructions).

### 5.1.3 **Non-Serious Adverse Events of Special Interest (Immediately Reportable to the Sponsor)**

Non-serious AEs of special interest are required to be reported by the investigator to the Sponsor immediately (i.e., no more than 24 hours after learning of the event; see Section 5.3.8 for reporting instructions). AEs of special interest for this study include the following:

- Cases of an elevated ALT or AST in combination with either an elevated bilirubin or clinical jaundice, as defined in Section 5.3.5.6.
- Suspected transmission of an infectious agent by the study drug, as defined below:  
Any organism, virus, or infectious particle (e.g., prion protein transmitting transmissible spongiform encephalopathy), pathogenic or non-pathogenic, is considered an infectious agent. A transmission of an infectious agent may be suspected from clinical symptoms or laboratory findings that indicate an infection in a HV/patient exposed to a medicinal product. This term applies only when a contamination of the study drug is suspected.

## 5.2 SAFETY PLAN

### 5.2.1 **Management of Specific Adverse Events**

- *Close monitoring of flu-like symptoms:* TLR7 agonists can be associated with dose-dependent flu-like symptoms; a percentage of HVs/patients may develop fever, chills, fatigue, myalgia, malaise, and headache within several hours after the dosing with RO7020531/*placebo*. Symptomatic treatment with acetaminophen (paracetamol) is recommended in case these events occur. There is an optional overnight stay in the clinical unit on Day 1 at the discretion of the Investigator for monitoring patients in Cohort 4 who develop flu-like symptoms/pyrexia during the first 12 hours post-dosing and do not respond to symptomatic treatment with acetaminophen (paracetamol). Additionally, the safety monitoring after dosing on Day 3 and Day 5 can be extended from 8 to 12 hours, at the discretion of the Investigator, in patients from Cohort 4 who develop flu-like symptoms/pyrexia and do not respond to symptomatic treatment. If at any time patients develop flu-like symptoms with pyrexia Grade 2 or above per DAIDS grading scale (38.6 °C or 101.5 °F), it is recommended that they call the site so that the Investigator can advise whether the patient needs to attend an unscheduled visit or receive symptomatic treatment with acetaminophen (paracetamol) up to 2 g/day.

- [REDACTED]  
[REDACTED]  
○ [REDACTED]

○

[REDACTED]

[REDACTED]

[REDACTED]

[REDACTED]

○

[REDACTED]

○

[REDACTED]

[REDACTED]

[REDACTED]

- For abnormal liver function tests in CHB patients (Part 2), see Section 5.3.5.6. For the drug discontinuation in patients with abnormal liver function tests, see Section 4.7.1.1.

---

 Based either on central laboratory (as per the SoA in Appendix 1) and/or local laboratory if performed for patient management and/or decision making. In such a scenario, if local laboratory tests are performed, an additional sample will be sent to the central laboratory, but decisions will be based on local laboratory results.

Liver Flare Monitoring: Liver flares, identified by an abrupt elevation of serum ALT, are acute hepatitis exacerbations due to changes in the immune response against HBV and its downstream mechanisms. These flares will be monitored for the duration of the study in Part 2. ALT elevations of 2 to 3 times the baseline value that are self-limited are likely to reflect a treatment response rather than drug toxicity. Progressive increases, increases inconsistent with the time course of a “flare” or ALT elevations associated with increases in bilirubin and alkaline phosphatase should be treated as AE. The Investigator should aim to exclude development of decompensated liver disease. Patients who develop signs of decompensated liver disease (e.g., ascites, varices, Child-Pugh Class B or C clinical classification ([Appendix 3](#)) should discontinue study treatment (Section [4.7.1.1](#)). Patients who develop flares should be monitored more closely with additional unscheduled visits and laboratory assessments.

No dose modification of RO7020531/placebo for *liver-related safety* is expected in Part 2 Cohort 4. No abnormal liver laboratory parameters were observed in Cohorts 1 to 3, including in those subjects with flu-like symptoms. At the discretion of the Investigator, study treatment can be discontinued. For the treatment stopping rules in individual HVs/patients and dose escalation stopping rules, please see Sections [3.1.2](#) and [4.7.1.1](#).

For the management of NUC analogue-related AE, please refer to the corresponding label.

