#### **4.6.1.5 Laboratory Assessments**

Normal ranges for the study laboratory parameters must be supplied to the Sponsor before the study starts. Laboratory safety tests shall be collected at time-points specified in the SoA ([Appendix 1](#)). Results of clinical laboratory testing will be recorded on the eCRF or will be received as electronically produced laboratory reports submitted directly from the local or central laboratory.

Additional blood or urine samples may be taken at the discretion of the Investigator if the results of any test fall outside the reference ranges, or clinical symptoms necessitate additional testing to monitor HV's/patients' safety. In the event of unexplained abnormal clinically significant laboratory test values, the tests should be repeated immediately and followed up until the values have returned to the normal range and/or an adequate explanation of the abnormality is found.

In Part 2 Cohorts 1, 2 and 3, only a central laboratory will be used; however, unscheduled local laboratory tests may be ordered per Investigator discretion. In this case, a duplicate sample should simultaneously be sent to the central laboratory for analysis.

In Part 2 Cohort 4 at the Day -1 (baseline) visit, a duplicate sample will be taken for liver function tests (ALT) and sent to central laboratory and local laboratory. The local laboratory sample is required to confirm eligibility for liver function parameters before dosing a patient on Day 1. The local laboratory result will not be used for statistical analysis. In the rare event that a patient is deemed to be eligible for the study based on the results of the local test, but the central laboratory test results (conducted after the patient has been dosed) differ, the patient should continue on the study.

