##### **Part 2: Patients with Hepatitis B Virus**

All assessments must be performed as per SoA ([Appendix 1](#)). Assessments scheduled on the day of study treatment administration should be performed prior to administration of study treatment, unless otherwise noted in the detailed SoA ([Appendix 1](#)).

Safety and PK in the study will be monitored on an ongoing basis with individual data review for every patient.

There is no window for study visits during the 1st week of treatment period (Day -1, 1, 2, 3, 4, 7, 8). Visits Day 21/22 can be carried out on Day 19/20 or Day 23/24. The end of treatment visit can be conducted on Day 39/40 or 41/42. In Cohort 4, there is no window for the Day 5 visit and visits introduced for viral load assessment (Days 15, 28, 35) have a window of  $\pm 2$  days.

If a patient misses a visit, the Investigator should contact the Sponsor immediately to discuss the visits and assessments to be performed for the patient to ensure that safety is monitored and that appropriate laboratory samples (including safety, PK and PD) are taken based on each patient's schedule.

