### **4.6.2.4 Assessments at Early Termination and Unscheduled Visits**

Please see [Appendix 1](#) for assessments that are required to be performed in case of an unscheduled visit.

If an unscheduled visit is required for safety reasons, necessary assessments will be undertaken at the discretion of the Investigator. All unscheduled assessments should be reported in eCRF.

Unscheduled local laboratory tests may be ordered per Investigator's discretion and may be used for the individual management of the HV/patient. A duplicate sample should simultaneously be sent to the central laboratory for analysis.

In case of early termination of a subject in MAD portion of Part 1, a blood sample for PK assessment may be collected at the time of discontinuation. In case of premature study drug discontinuation in Part 2 (Section [4.7.1.1](#)), a patient should be called for an unscheduled visit and assessments should be performed as listed in the SoA ([Appendix 1](#)) under "Study Drug Discontinuation", including physical examination, vital signs, ECG, safety labs, HBV parameters and PD assessments.

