#### **5.3.1 Adverse Event Reporting Period**

Investigators will seek information on AEs at each HV/patient contact. All AE, whether reported by the HV/patient or noted by study personnel, will be recorded in the HV's/patient's medical record. AEs will then be reported on the AE eCRF as follows:

**After informed consent** has been obtained **but prior to initiation of study drug**, only SAEs caused by a protocol-mandated intervention should be reported (e.g., SAE related to invasive procedures such as biopsies). Any other AE should not be reported.

**After initiation of study drug**, all AE, regardless of relationship to study drug, will be reported until the end of follow-up, which is 28 days after the last dose for HVs and 6 weeks after the last dose for patients.

**After the end of follow-up period** (28 days after last dose for HVs and 6 weeks after last dose for patients), investigators should report any deaths, SAE, or other AE of concern that are believed to be related to prior treatment with study drug (see Section 5.5).

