### **6.7.2 Clinical Laboratory Test Results**

All clinical laboratory data will be stored on the database in the units in which they were reported. HV's/patient's listings and summary statistics at each assessment time will be presented using the International System of Units (SI units; Système International d'Unités). Laboratory data not reported in SI units will be converted to SI units before processing.

Laboratory test values will be presented by individual listings with flagging of values outside the normal ranges.

Safety analyses to determine if treatment groups are safe to proceed will use all available data reported from local and/or central laboratory results. Unscheduled local laboratory tests may be ordered per investigator discretion and may be used for the individual management of the HV/patient. A duplicate sample should simultaneously be sent to the central laboratory for analysis (Part 2 only).

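### In Cohort 4, adding a liver panel to the existing Day 15, 28 and 35 blood draws would cut the longest scheduled on-treatment ALT gap from 20 days to 7

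*Combined protocol and SAP*

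**What the plan says.** Section 5.2.1 identifies a flare by an abrupt ALT rise and judges it by its course. A self-limited rise to two or three times baseline is read as probable treatment response. A progressive rise, or one that does not fit the time course of a flare, is handled as an adverse event. The commitment is that "These flares will be monitored for the duration of the study in Part 2"; no ALT interval is given there.

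The interval comes from Appendix 1. ALT belongs to the blood chemistry panel (section 4.6.1.5). Both Cohort 4 tables, summary and detailed, mark on-treatment chemistry at Days 2, 5, 8, 21 and 41, then at Weeks 9 and 12. Days 15, 28 and 35 carry vital signs and blood for HBV DNA, with no chemistry. Section 4.6.2.2 describes these as "visits introduced for viral load assessment (Days 15, 28, 35) have a window of" ±2 days.

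Other testing is possible:
- Section 4.6.1.5: "Additional blood or urine samples may be taken at the discretion of the Investigator if the results of any test fall outside the reference ranges"; symptoms are a second prompt.
- Section 5.2.1: "Patients who develop flares should be monitored more closely with additional unscheduled visits and laboratory assessments".
- Section 6.7.2 (and similarly 4.6.2.4): "Unscheduled local laboratory tests may be ordered per investigator discretion".
- Section 4.6.2.2: safety and PK are "monitored on an ongoing basis with individual data review for every patient".
- Section 5.3.1: "Investigators will seek information on AEs at each HV/patient contact".

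Section 4.7.1.1 requires discontinuation for confirmed ALT of at least 10×ULN, for ALT above 5×ULN with raised bilirubin, and for ALT above 5×ULN with INR above 1.5.

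**The concern.** The rules above need serial ALT results, and after Day 8 the schedule supplies two during treatment. None of the other provisions ensures an ALT in a patient who feels well between Day 21 and Day 41. Some respond to an abnormal result, symptoms or a known flare, some permit a test without requiring one, and data review cannot cover a sample that was not taken.

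The Day 41 sample is drawn before dosing (Appendix 1, Cohort 4, note j), so at nominal days it can spare only the last planned dose. Day 21 is thus the last scheduled ALT that can materially change exposure.

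This matters most in Cohort 4. Section 3.2.2.2 expects virologically suppressed patients to flare less than those with significant viral loads. Cohort 4 patients must be viraemic, take no NUC and may enter with ALT up to 5×ULN. The absence of abnormal liver results noted in section 5.2.1 comes from Cohorts 1 to 3, who were suppressed. Safety is the primary objective of Part 2.

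**Working it through.** **Inputs.** Chemistry days and HBV DNA days: Appendix 1, Cohort 4. Windows (section 4.6.2.2): Day 21 may fall on Day 19, 21 or 23; Day 41 on Day 39 or 41; Days 15, 28 and 35 within ±2 days; Day 8 has none. Dosing: every other day (QOD), Days 1 to 41 (section 4.4.2.1).

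**The plan's own figure.** QOD doses = (41 − 1)/2 + 1 = 21, matching the stated maximum. The plan gives no flare duration, onset pattern or target ALT interval.

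**Gaps now.**
- Day 8 to 21: 13 days (8 to 19 = 11; 8 to 23 = 15).
- Day 21 to 41: 20 days (23 to 39 = 16; 19 to 41 = 22).

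**Doses between the last two draws.** Draws precede dosing, so these are Days 21, 23, …, 39 = 10 doses. With windows the range is 8 (Days 23–37) to 11 (Days 19–39). On weekly dosing synchronised with Days 21, 28 and 35, it is 3.

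**Gaps with draws added at Days 15, 28 and 35.** Nominal: 7, 6, 7, 7, 6. The largest with windows is 11 days (for example Day 19 to 30).

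**Illustrative share missed.** Assume a silent rise lasting L days with onset uniform over the span between the first and last draw. Then

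share missed = Σ max(0, gap − L) / span.

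| L (days) | Now, Days 8–41 (gaps 13, 20) | Now, Days 1–41 (gaps 1, 3, 3, 13, 20) | With added draws, nominal | With added draws, worst windows |
|---|---|---|---|---|
| 7 | (6+13)/33 = 57.6% | 19/40 = 47.5% | 0% | 7/31 = 22.6% |
| 10 | (3+10)/33 = 39.4% | 13/40 = 32.5% | 0% | 1/31 = 3.2% |
| 14 | 6/33 = 18.2% | 6/40 = 15.0% | 0% | 0% |
| 20 | 0% | 0% | 0% | 0% |

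The Days 1–41 column includes the densely sampled first week. The worst-window column covers all 5×3×5×5×2 = 750 permitted combinations; the 22.6% arises at Days 8, 13, 23, 26, 37, 39. Across the six permitted combinations of the current schedule, the 7-day figure is 54.8% to 57.6%. With a 22-day gap (draws at Days 8, 19, 41), the current schedule misses 8/33 = 24.2% of 14-day rises and 1/33 = 3.0% of 21-day rises.

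**Mean time from onset to next draw** = Σ gap² / (2 × span), over Days 8–41.
- Now: (169 + 400)/66 = 8.6 days (7.8 to 9.2 with windows).
- With added draws: (49 + 36 + 49 + 49 + 36)/66 = 3.3 days (worst 4.2).

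**Who could benefit.** Section 1.2.2 reports nine Cohort 4 patients dosed by 01 May 2020, out of up to 15. That leaves at most 15 − 9 = 6 patients and 6 × 3 = 18 extra panels.

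**The case against.** A reader might infer that the plan breaks its own promise to monitor flares throughout Part 2. It does not: the sentence sets no frequency. The on-treatment chemistry days are those of Cohorts 1 to 3 with Day 5 added, and no text requires weekly or two-weekly ALT.

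The discretionary routes are also wider than symptoms alone. A patient entering above the reference range already qualifies for extra sampling under section 4.6.1.5. The patient least covered is the one with normal scheduled results and no symptoms, although even for the others the test remains optional.

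Section 1.2.2 reports, up to 01 May 2020, no clinically significant change in safety parameters, laboratory assessments included, apart from one transient cytopenia. That is reassuring and should be weighed. But it is not explicit that the statement covers Cohort 4, and Cohort 4 data would come from this same sparse schedule.

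It is tempting to read 58% as the proportion of flares missed, or ten doses as expected harm. Neither follows. Duration and onset are assumed, the figure covers any silent rise, and section 5.2.1 regards many modest rises as benign. The ten doses matter only if a silent rise meets a stopping criterion, and the documents give no probability for that.

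Finally, part of section 5.2.1 is redacted, and a surviving footnote mentions local laboratory results used for decisions. If the hidden text already requires ALT in well patients near these days, the point falls. The schedule tables themselves are not redacted.

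**Conclusion.** This is a cheap improvement to a design choice, not a breach or an error. The gaps of 13 and 20 days (up to 15 and 22) and the ten intervening QOD doses follow directly from the schedule and need no assumption about flares. A rise lasting 20 days or more (22 with windows) always meets a scheduled draw, though possibly about three weeks after onset. A shorter silent rise can be missed altogether. In either case the early course that section 5.2.1 relies on may go unrecorded, and the ALT stopping rules receive no scheduled result between Day 21 and the draw before the last dose. The miss rates are illustrations only.

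The change is worth making because it uses blood draws that already take place. Confidence is medium, given the redaction and the small number of patients left. The point concerns on-treatment sampling only.

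**What to change.** For the remaining Cohort 4 patients, add ALT, AST, total and indirect bilirubin, ALP and INR to the existing Day 15, 28 and 35 draws, taken before any dose that day. INR is included because section 4.7.1.1 pairs it with ALT above 5×ULN; a reflex INR when ALT is Grade 3 or higher would also serve. No threshold, dose or stopping rule changes. In the report, state that later Cohort 4 patients were sampled more densely, and also summarise ALT at the common days (8, 21 and 41).

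The cost is an amendment to the Schedule of Assessments with the approvals required by section 9.5, revised consent and re-consent (section 8.2), and slightly more blood and laboratory work. There is no new visit or needle stick. ALT ascertainment becomes uneven within Cohort 4, and between Cohort 4 and Cohorts 1 to 3; the common-day summary addresses this. If approvals take time, fewer than six patients will benefit.
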